8.6.3 Analysis of secondary efficacy endpoint(s)

The key secondary efficacy endpoints are:

- Change from baseline in itch-related quality of life at the end of Week 12, as assessed by the total Skindex-10 scale score;
- Change from baseline in itch-related quality of life at the end of Week 12, as assessed by the total 5-D Itch scale score;
- Proportion of patients achieving an improvement from baseline ≥ 3 points with respect to the weekly mean of the daily 24-hour Worst Itching Intensity NRS score at Week 12 of the Treatment period.

The Skindex-10 scale total score and the 5-D Itch total scale score will be analyzed using MMRM that will contain treatment, week, and treatment-by-week interaction as fixed effects; baseline score and renal disease status as covariates. Repeated measures will include values that reflect the Skindex-10 and 5-D total score at the end of weeks 4, 8, 10, and 12. The total score derivation for Skindex-10 and 5-D Itch scale detailed in [Appendix B](#) and [Appendix C](#) respectively.

The baseline value will be defined as the value of the Skindex-10 or 5-D Itch total score collected on Day 1 prior to randomization. Missing Skindex-10 Itch scale and 5-D Itch scale

Statistical Analysis Plan (SAP)

total scores will be imputed in a similar fashion as the primary endpoint for the MMRM analyses using the MI approach assuming data is missing at random. The mean treatment difference between each CR845 dose and placebo, and between all CR845 doses combined and placebo will be estimated as the simple contrast in the treatment effect at Treatment period week 12.

Descriptive statistics will be provided for the observed value and change from baseline at week 12 by treatment group for Skindex-10 scale and the 5-D Itch total scores. The adjusted LS means and SE from the model will be presented for each treatment group. The LS means estimate for the difference, standard error, 95% CI, and p-value will be presented. The analysis will be conducted using the Full Analysis Set.

An unstructured covariance matrix structure will be used to model the within patient errors. If there are convergence issues, other structures that require fewer parameters will be applied in the following order: 1) heterogeneous Toeplitz, 2) autoregressive, 3) compound symmetry until convergence is attained. The Kenward-Roger approximation will be used to estimate the denominator degrees of freedom.

Descriptive statistics for the change from baseline with respect to the Skindex-10 and the 5-D Itch total score will also be provided by treatment group for each renal disease category (moderate CKD non-dialysis; severe CKD non-dialysis; severe CKD on dialysis). In addition, an analysis of these key secondary endpoints by renal disease status will be performed using an MMRM model and a treatment of missing data similar to the one described above.

A linear trend test across the doses based on a MMRM model will also be presented to explore the dose response curve. The model will contain treatment as continuous variable (Placebo = 0 mg and other doses 0.25, 0.5, and 1.0 mg), week, and treatment-by-week interaction as fixed effects; baseline score and renal disease status as covariates. The estimate and p-value for overall effect of dose will be provided. An unstructured covariance matrix structure will be used to model the within patient errors.

Patients achieving improvement from baseline ≥ 3 points will be summarized using count and percentage. The proportion of patients achieving an improvement from baseline ≥ 3 points with respect to the weekly mean of the daily 24-hour Worst Itching Intensity NRS score at week 12 of the treatment period will be analyzed using logistic regression with terms for treatment group, baseline NRS score, and renal disease status. Odds ratio, and P-value based on logistic regression comparing difference in patients achieving NRS response between CR845 treatment group and placebo and between all CR845 doses combined and placebo at week 12 will be presented. In case of small counts resulting in separation issues of the log-likelihood, Firth's correction will be applied.

Statistical Analysis Plan (SAP)

Missing NRS data will be imputed using the same methodology described for the primary efficacy endpoint. Specifically,

- The proportion of patients who have an improvement from baseline with respect to the weekly mean of the daily 24-hour Worst Itching Intensity NRS score ≥ 3 points will be calculated for each imputed dataset derived for the primary efficacy analysis. Differences between each CR845 treatment group and placebo will be compared using a logistic regression model containing terms for treatment group, baseline NRS score and renal disease status. P-value will be presented.
- Results of the logistic regression on the multiply imputed data sets will be summarized by the SAS MIANALYZE procedure (see [Appendix I](#)).
- For comparisons between treatments at end of treatment (not using MI), the same logistic regression will be performed on observed data with additional non-parametric analyses evaluating pairwise treatment differences will be tested using the Cochran-Mantel-Haenszel test, adjusting for strata (i.e renal disease status). An exact test of whether the common odds ratio across strata equals 1 will be used if the observed count in a particular cell is small (ie, <5) (see [Appendix J](#)).

The proportion of patients achieving an improvement from baseline ≥ 3 points by each renal disease category (moderate CKD non-dialysis; severe CKD non-dialysis; severe CKD on dialysis) will be presented. In addition, treatment differences within each subgroup will be investigated using logistic regression, including a Fisher's exact test for the end of treatment (not using MI) comparison.

The proportion of patients achieving an improvement from baseline ≥ 3 points with respect to the weekly mean of the daily 24-hour Worst Itching Intensity NRS score at week 12 of the Treatment period will be also be analyzed using logistic regression with terms for treatment group as continuous variable (Placebo = 0 mg and other doses 0.25, 0.5, and 1.0 mg), baseline NRS score, and renal disease status to evaluate the dose response curve. Overall effect of treatment group will be presented.

Listings will be provided for all the collected Skindex-10 scale score and the 5-D Itch Scale score separately.

8.6.4 Analysis of additional efficacy endpoint(s)

Itch-intensity Measures:

- Proportion of patients who have an improvement from baseline at week 12 of the treatment period with respect to the weekly mean of the 24-hour Worst Itching Intensity NRS scores ≥ 1 , ≥ 2 , and ≥ 4 points will be calculated. Treatment differences

Statistical Analysis Plan (SAP)

will be compared using a logistic regression model with terms for treatment group, baseline NRS score and renal disease status. This analysis will be conducted separately for each NRS score categories (≥ 1 vs < 1 (no or less improvement compared to baseline, or, ≥ 2 vs < 2 , and ≥ 4 vs < 4 points). The calculation of the proportions will be based on the NRS data using an MI approach for the missing data as in the primary efficacy analysis. Results of the logistic regression on the multiple imputed data sets will be summarized by the SAS MIANALYZE procedure. In addition, a graph showing the proportion of patients who have an improvement from baseline in NRS scores at week 12 that are ≥ 1 , ≥ 2 , ≥ 3 , and ≥ 4 will be prepared. For comparisons between treatments at end of treatment (not using MI), the same logistic regression will be performed on observed data with additional non-parametric analyses evaluating pairwise treatment differences pairwise treatment differences will be tested using the Cochran-Mantel-Haenszel test, adjusting for strata (i.e renal disease status). An exact test of whether the common odds ratio across strata equals 1 will be used if the observed count in a particular cell is small (ie, < 5).

- Proportion of “complete responders” with respect to Worst Itching Intensity score NRS at week 12 and end of treatment. A patient that has $\geq 80\%$ of the non-missing daily NRS scores in a week equal to 0 or 1 is considered a complete responder at that week. Patients with < 4 non-missing NRS scores within a week will be derived as missing at that week. Treatment differences will be compared using a logistic regression model with terms for treatment group, baseline NRS score and renal disease status. In addition, pairwise treatment differences will be tested using the Cochran-Mantel-Haenszel test, adjusting for strata (i.e renal disease status). An exact test of whether the common odds ratio across strata equals 1 will be used if the observed count in a particular cell is small (ie, < 5).
- Change from baseline in the weekly mean of the 24-hour Worst Itching Intensity NRS score at each post baseline week (except week 12) of the treatment period will be summarized. Treatment differences between CR845 and placebo at each post baseline time point will be evaluated and presented using the same MMRM detailed in primary efficacy analysis (see [section 8.6.2](#)). Analysis will be based on the NRS data using an MI approach for the missing data as in the primary efficacy analysis.
- Proportion of patients who rate their itch condition as “Very much improved” or “Much improved” at the end of week 12 of the treatment period and end of treatment, as measured by the Patient Global Impression of Change (PGIC). Treatment differences will be compared using a logistic regression model with terms for treatment group, baseline Patient Global Impression Worst Severity score and renal disease status. In addition, pairwise treatment differences will be tested using the

Statistical Analysis Plan (SAP)

Cochran-Mantel-Haenszel test, adjusting for strata (i.e renal disease status). An exact test of whether the common odds ratio across strata equals 1 will be used if the observed count in a particular cell is small (ie, <5). The PGIC responses at week 12 and end of treatment will also be presented with count and percentage.

- The number and percentage of patients in each of the 5 categories of the Patient Global Impression of Worst Itch Severity at baseline and at each scheduled post baseline week of the treatment period will be tabulated. In addition, the proportion of patients who have at least 1-point improvement or more from baseline at each week of the Treatment Period, as measured by the Patient Global Impression of Worst Itch Severity will be calculated. Similarly, the proportion of patients who indicate a Patient Global Impression of Worst Itch Severity of 'None' will be derived at Week 12 and end of treatment. Treatment differences will be compared using a logistic regression model with terms for treatment group, baseline Worst Itch Severity and renal disease status. In addition, pairwise treatment differences will be tested using the Cochran-Mantel-Haenszel test, adjusting for strata (i.e renal disease status). An exact test of whether the common odds ratio across strata equals 1 will be used if the observed count in a particular cell is small (ie, <5).

Itch-related Quality-of-Life Measures:

- Change from baseline in itch-related quality of life at each scheduled post baseline week of the Treatment period, as assessed by the total score of the 5-D itch scale. Treatment differences between each CR845 dose group and placebo at each post baseline time points will be evaluated and presented (except week 12) using the MMRM fitted for the secondary efficacy analysis [section 8.6.3](#).
- The proportion of patients who either rate the degree of itching intensity as 'Not Present' or the direction of itching as 'Completely Resolved' over the past 2 weeks from the 5-D Itch Scale will be calculated at Week 12 and end of treatment. Treatment differences will be compared using a logistic regression model with terms for treatment group, baseline 5-D Itch Total Score and renal disease status. In addition, pairwise treatment differences will be tested using the Cochran-Mantel-Haenszel test, adjusting for strata (i.e renal disease status). An exact test of whether the common odds ratio across strata equals 1 will be used if the observed count in a particular cell is small (ie, <5).
- The proportion of patients with itching present at each body part will be presented at Week 12 and end of treatment along with the shift from baseline (Present or Not Present combinations). The presence of itching at each body part at end of treatment will be compared between treatments adjusting for strata (i.e renal disease status) and presence of itch at baseline (Present/Not Present). An exact test of whether the

Statistical Analysis Plan (SAP)

common odds ratio across strata equals 1 will be performed.

- Change from baseline in itch-related quality-of-life at each week of the Treatment period, as assessed by the total score of the Skindex-10 Scale. Treatment differences between each CR845 dose group and placebo at each scheduled post baseline time points will be evaluated and presented (except week 12) using the same MMRM fitted for the secondary efficacy analysis [section 8.6.3](#).
- The total Skindex-10 score is subdivided into 3 domain scores, which are sums of the scores of the following consideration of questions ([Appendix B](#)): disease domain (questions 1 to 3), mood/emotional distress domain (questions 4 to 6), and social functioning domain (questions 7 to 10). Change from baseline in itch-related quality of life at each of the post baseline weeks of the treatment period with respect to each of the 3 domains of the Skindex-10 Scale will be calculated. Treatment differences with respect to each domain will be evaluated using a model similar to the MMRM fitted for the analysis of the change from baseline in the total score of the Skindex-10 Scale.
- Change from baseline in itch-related quality of life at week 12 of the treatment period and at each of the remaining weeks of the treatment period with respect to each of the domains of 5-D Itch scale. Treatment differences with respect to each domain will be evaluated using a model similar to the MMRM fitted for the analysis of the change from baseline in the total score of the 5-D Itch Scale. The domain score derivation will be considered as detailed in the [Appendix C](#).

Listings will be provided for the variables used in the additional efficacy endpoints (which are not mentioned in the primary or secondary analysis).

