6.2 Full Analysis Set (FAS)

The full analysis set is defined as all randomized patients who received at least 1 dose of study drug. Patients in the full analysis set will be analyzed according to their randomized treatment, regardless of the actual treatment received. The Full Analysis set will be used to analyze all efficacy endpoints.

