8 STATISTICAL METHODS

8.1 General statistical conventions

All statistical procedures will be completed using SAS version 9.2 or higher.

Unless otherwise noted, continuous variables will be summarized using descriptive statistics, including number of patients with non-missing observation (n), mean, median, standard deviation (SD), minimum (min) and maximum (max). Means and medians will be reported to one decimal place more than the raw data. Standard deviation will be reported to two more decimal places than the raw value. The minimum and maximum will be reported to the same decimal as the raw data.

Categorical variables will be summarized using the frequency count and the percentage of patients in each category. All percentages will be rounded to one decimal point. The number and percentage of patients will always be presented in the form XX (XX.X%) where the percentage is in parentheses. To ensure completeness, all summaries for categorical and discrete variables will include all categories, even if none of the patients in a particular category. Counts of zero in any category will be presented as “0”. Unless otherwise noted, for all percentages, the number of patients in the analysis population for the treatment group will be the denominator.

“Baseline” will be defined as per [section 7.1](#). For efficacy endpoints, “on-treatment” is defined as any assessment following the first dose of study drug and within 2 days from the last dose of study drug recorded in the patient diary. For safety endpoints (excluding adverse events), any assessment within 7 days after last dose of study drug will be deemed “on-treatment”. For all endpoints “End of treatment” (EOT), in summaries, will be represented by the last non-missing on-treatment value recorded up to and including the Week 12/Early Termination visit. Treatment emergence for adverse events is described in [section 8.7.1](#). Summaries will be presented across all scheduled visits and EOT unless stated otherwise. Only on-treatment data will be used in summaries and statistical analyses (with the exception of the Patient Global Impression of Change).

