8.6.2 Analysis of primary efficacy endpoint

The primary efficacy endpoint is defined as the change from baseline to week 12 of the Treatment period with respect to the weekly mean of the daily 24 hour Worst Itching Intensity NRS score. Testing of the primary efficacy endpoint will be 2-sided and conducted at the 5% error level.

The study will be considered positive if at least one safe and efficacious dose is identified. Effectiveness will be evaluated based on results of the primary efficacy analysis either using the estimate of treatment effect or the p-value of the hypothesis tests.

The null hypotheses H_{01} , H_{02} , H_{03} , and H_{04} given below will be tested against the alternative hypotheses H_{A1} , H_{A2} and H_{A3} respectively:

$$\begin{array}{llll} H_{01}: \mu_{D1} - \mu_P = 0, & H_{02}: \mu_{D2} - \mu_P = 0, & H_{03}: \mu_{D3} - \mu_P = 0, & H_{04}: \mu_{D123} - \mu_P = 0 \\ H_{A1}: \mu_{D1} - \mu_P \neq 0, & H_{A2}: \mu_{D2} - \mu_P \neq 0, & H_{A3}: \mu_{D3} - \mu_P \neq 0, & H_{A4}: \mu_{D123} - \mu_P \neq 0 \end{array}$$

Where μ_{D1} , μ_{D2} and μ_{D3} denote the mean change in Worst Itching Intensity NRS score from baseline to week 12 in the three active treatment dose groups and μ_P denotes the mean change from baseline to week 12 in the placebo group (placebo, P). D_1 denotes the CR845 0.25mg dose group, D_2 denotes the CR845 0.5mg dose group and D_3 denotes the CR845 1mg dose group and D_{123} denotes the doses (0.25, 0.5 and 1 mg) combined.

The weekly mean of the 24-hour Worst Itching Intensity NRS score will be defined as the sum of the daily Worst Itching Intensity NRS score reported during a specific week of the Treatment period (eg, Days 1 to 7, Days 8 to 14, Days 15 to 21, etc. till 78 to 84) divided by the number of non-missing scores for that week. If there are <4 non-missing daily worst itching scores during a specific week, the corresponding weekly mean worst itching score will be set to missing. The baseline score will be defined as the average of the daily 24-hour Worst Itching Intensity NRS scores over the last 7 days prior to randomization; at least 4 completed Worst Itching Intensity NRS worksheets will be required prior to randomization.

The primary efficacy variable will be analyzed using a mixed effects model with repeated measures (MMRM). The model will contain treatment, week, and treatment-by-week interaction as fixed effects; baseline score and renal disease status as covariates. For each

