9 CHANGES TO PLANNED ANALYSIS FROM STUDY PROTOCOL

- Antipruritic medications are not identified in the CRF or the database using a Yes/No flag. The use of antipruritic medications will need to be derived based on the indication entered on the CRF. Therefore, a specific analysis of antipruritic medications by ingredient will not be completed since it will not be different than the analysis summarizing medications by preferred term.
- Section 8.6.1 of the protocol defines the primary endpoint as follows: “The weekly mean of the 24-hour Worst Itching Intensity NRS score will be defined as the sum of the daily Worst Itching Intensity NRS score reported during a specific week during the Treatment Period (eg, Days 2 to 8, Days 9 to 15, Days 16 to 22, etc.) divided by the number of days with non-missing scores for that week. If the daily worst itching score is missing for >3 days during a specific week, the corresponding weekly mean worst itching score will be set to missing.”. However, to facilitate patient diary dates anomalies which may result in duplicate dates (e.g. patient completes diary shortly after midnight and then again on same date) and the fact that only the diary date is used for mapping to a specific week as per [section 7.1](#), of this SAP, the underlined text above is replaced with “...divided by the number of non-missing scores for that week. If there are <4 non-missing daily worst itching scores during a specific week...”. In addition, because in this study the Day 1 NRS score is planned to be taken after dosing, weeks are re-defined in this SAP one day earlier than stated in the protocol (eg. Days 1 to 7, Days 8 to 14, Days 15 to 21, etc.).
- Section 8.6.2 of the protocol states that missing Skindex-10 Itch Scale and 5-D Itch Scale total scores will not be imputed. To ensure a more unbiased assessment of these secondary endpoints, which does not ignore missing data, analyses in this SAP state that the same MI method with MAR assumption will be applied to these endpoints in similar fashion to the primary endpoint.

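### The Week 12 tests of complete response and the other non-imputed itch responder endpoints drop patients with no Week 12 value, while the tables keep them in the denominator

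*SAP*

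**What the plan says.** **Endpoints.** SAP 8.6.4 tests several binary outcomes by logistic regression and by CMH (or an exact test when cells are small).
- Complete response requires at least 80% "of the non-missing daily NRS scores in a week equal to 0 or 1 is considered a complete responder at that week". For this endpoint, "Patients with < 4 non-missing NRS scores within a week will be derived as missing at that week".
- Worst itch severity of 'None' "will be derived at Week 12 and end of treatment". Improvement of at least 1 point on the same scale is assessed at each week.
- The 5-D outcome (degree 'Not Present' or direction 'Completely Resolved') "from the 5-D Itch Scale will be calculated at Week 12 and end of treatment".

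**Missing data.** SAP 7.2.1 limits multiple imputation to the weekly mean NRS and the Skindex-10 and 5-D totals. The NRS-improvement responders at Week 12 inherit it through 8.6.3 and 8.6.4. The outcomes listed above do not.

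**Which data count.** SAP 8.1 admits only on-treatment efficacy data, up to 2 days after the last dose, with PGIC excepted. SAP 8.6 stops at the date of treatment discontinuation. SAP 7.3 maps an early termination visit to Week 12 only within 2 days of the planned day.

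**End of treatment (EOT).** Under SAP 8.1 it "will be represented by the last non-missing on-treatment value recorded up to and including the Week 12/Early Termination visit".

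**Population and denominator.** SAP 6.2: "The Full Analysis set will be used to analyze all efficacy endpoints". SAP 8.1 makes the analysis-population N the default denominator for every percentage.

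**The concern.** A responder analysis has to say what a patient who stopped the drug counts as. For these endpoints the SAP gives three answers, and 8.6.4 does not acknowledge the difference. In the Week 12 tests the patient is absent. In the Week 12 percentages, under the default denominator, the patient is present and not a responder. At EOT the patient is whatever the last on-treatment value says, so someone who met the criterion in the last evaluable week and then stopped for an adverse event is a success.

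Two things follow. A p-value printed beside a percentage may describe a different set of patients. And if one arm loses more patients, the Week 12 test removes more of that arm's potential failures, while the EOT test may credit some of them as responders.

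Elsewhere the SAP handles such patients explicitly. Sensitivity analysis 2 of the primary endpoint imputes adverse-event stoppers from the baseline distribution trimmed to 5 to 10. A complete responder's weekly mean cannot be that high: with 4 of 5 scores at 1 and one at 10, the largest possible mean is (4 × 1 + 10)/5 = 2.8. Complete response has no counterpart to that analysis.

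**Working it through.** **1. Plan's own figure.** There is none for these endpoints. The power table in SAP 5 concerns the primary endpoint, and nothing below depends on it.

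**2. Who has a Week 12 value.** Week 12 is the last diary week (SAP 8.6.2: "Days 15 to 21, etc. till 78 to 84").
- Complete response: four daily scores need data through at least Day 78 + 3 = 81. Under the 2-day rule in 8.1 the last dose must fall on or after Day 81 − 2 = 79. Under the 8.6 cut-off it must be Day 81. Duplicate diary dates, which SAP 9 mentions, could shift this slightly.
- Severity and 5-D: an early termination visit counts as Week 12 only on Days 84 ± 2, that is 82 to 86. With the 2-day rule, the last dose must be on or after Day 82 − 2 = 80.

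Anyone stopping earlier has no Week 12 value and leaves the tests. A completer with fewer than four Week 12 diary scores also leaves the complete-response test. The accurate label is therefore observed-case, not completers-only.

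**3. Tested set against all FAS patients.** All rates here are assumptions. Take response among observed patients as 15% on placebo and 30% on a dose, and let d be the proportion without a Week 12 value.

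Rate over all FAS patients = observed rate × (1 − d). Odds ratio = [p₁/(1 − p₁)] / [p₀/(1 − p₀)], unadjusted.

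In the tested set the difference is 30 − 15 = 15 points and the odds ratio is (0.30/0.70)/(0.15/0.85) = 2.43, whatever the dropout. Over all FAS patients:

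| d placebo / dose | Rates over all FAS | Difference | Odds ratio |
|---|---|---|---|
| 10% / 10% | 13.5% vs 27.0% | 13.5 | (0.270/0.730)/(0.135/0.865) = 2.37 |
| 10% / 20% | 13.5% vs 24.0% | 10.5 | (0.240/0.760)/(0.135/0.865) = 2.02 |
| 10% / 25% | 13.5% vs 22.5% | 9.0 | (0.225/0.775)/(0.135/0.865) = 1.86 |
| 20% / 10% | 12.0% vs 27.0% | 15.0 | (0.270/0.730)/(0.120/0.880) = 2.71 |

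Under the default denominator in 8.1, the rates in the second column are what the table would print. The test beside it would be run on 15% versus 30%.

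**4. False-positive rate.** Suppose success with stoppers counted as failures is truly equal in both arms. The observed-case rate is then that success rate divided by (1 − d). At 30% success with 10% and 20% dropout it is 0.30/0.90 = 33.3% versus 0.30/0.80 = 37.5%. A two-sample proportion test, simulated 200,000 times per scenario without covariates, favoured the dose falsely as follows (nominal 2.5%):

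| Dropout placebo / dose | True success | n = 60 per arm | n = 120 per arm |
|---|---|---|---|
| 10% / 10% | 15% or 30% | 2.4 to 2.6% | 2.5 to 2.6% |
| 10% / 20% | 15% | 4.9% | 6.0% |
| 10% / 20% | 30% | 5.9% | 8.7% |
| 10% / 30% | 15% | 8.0% | 13.2% |
| 10% / 30% | 30% | 16.2% | 27.5% |

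Counting stoppers as non-responders gave 2.3 to 2.6% throughout.

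**5. EOT version.** Assume 15% success among observed patients in both arms, 10% and 30% dropout, and 30% of stoppers meeting the criterion at their last on-treatment value.
- EOT, placebo: 0.90 × 0.15 + 0.10 × 0.30 = 16.5%
- EOT, dose: 0.70 × 0.15 + 0.30 × 0.30 = 19.5%
- Observed cases: 15% vs 15%
- Stoppers as non-responders: 0.90 × 0.15 = 13.5% vs 0.70 × 0.15 = 10.5%

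The sign of the difference depends on the rule.

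**The case against.** **Percentages.** A reader might infer that no planned output counts a stopper as a failure, or that a 15-point difference would be reported whatever the dropout. The default denominator in SAP 8.1 contradicts both: the displayed percentages already keep stoppers in the denominator. The defect is confined to the tests and their disagreement with the tables. The table shells are in a separate document and could specify otherwise, but the SAP text does not.

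**Direction.** It is tempting to say that the tests favour CR845. Protocol 4.3 lists dizziness, fatigue and somnolence among the most common adverse events, but no 12-week dropout rate is given. Protocol 4.2 and 7.2 describe these doses as well tolerated over about a week. An EOT stopper who was not responding counts as a failure. The direction is therefore conditional. With 20% dropout on placebo and 10% on the dose, the difference in points is the same in both sets.

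**Consistency.** SAP 9 explains its imputation of the Skindex-10 and 5-D totals thus: "To ensure a more unbiased assessment of these secondary endpoints, which does not ignore missing data". This covers secondary endpoints and is not a commitment for additional ones. A non-responder rule also differs from the imputation behind the NRS-improvement responders, so one stopper could be imputed as a 4-point responder and set to failure for complete response. That is a fair criticism of the rule, but it does not supply the missing one.

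**PGIC.** It is exempt from the on-treatment rule and is collected at early termination. SAP 4.3 defines it at Week 12/end of treatment as one time point; 8.6.4 lists the two separately. It is affected only if Week 12 excludes early-termination ratings.

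**Weight.** These are additional endpoints in a Phase 2 trial without multiplicity adjustment. That stands and sets the severity.

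**Conclusion.** The point holds as a minor one. As written, the Week 12 tests of complete response, worst itch severity (both forms) and the 5-D not-present-or-resolved outcome are observed-case, the percentages beside them use a different set of patients, and the EOT tests carry the last on-treatment value forward. No planned test treats stopping drug as non-response.

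Measured against that definition of response, the tests can be biased toward the arm that loses more patients. In the worked example with 10% and 25% dropout, 15 points in the tested set correspond to 9 points over all FAS patients. With equal dropout the false-positive rate stays near 2.5% in the favourable direction. Every dropout and response rate is assumed, and the simulation used an unadjusted test in place of the planned models.

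The documents do not support reading this as a threat to the trial's main conclusion. The primary endpoint, the key secondary endpoints and the NRS-improvement responders at Week 12 all use multiple imputation.

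**What to change.** In SAP 8.6.4, for complete response, worst itch severity ('None' and at least 1 point better) and the 5-D outcome:
- Add a Week 12 test that includes all FAS patients and counts as non-responders those who discontinued study drug before Week 12 or have no Week 12 value.
- Use the same denominator for the percentages and the test.
- Label the observed-case Week 12 and the EOT versions as supportive.

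Separately, reconcile SAP 4.3 with 8.6.4 on whether PGIC at Week 12 includes early-termination ratings, and SAP 8.1 with 8.6 on the last day of usable efficacy data.

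Imputing daily scores and deriving complete response from them would be closer to the NRS-improvement analyses, but is more work.

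Cost: SAP wording and one derivation flag, with no new data. Tested response rates become somewhat lower, and a few completers with lost diaries count as failures.
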